#### Part C (Pivotal)

Part C will be a randomized, double-blind, placebo-controlled evaluation of 100 mg of BIIB067 administered 8 times over approximately 24 weeks to approximately 99 participants with SOD1-ALS. Participants will be randomized to receive BIIB067 or placebo in a 2:1 (active:placebo) ratio. The primary analysis population (N = ~60) will comprise participants who meet prognostic enrichment criteria for rapid disease progression, defined as those with a prerandomization ALSFRS-R slope decline of at least 0.9/month OR a protocol-defined SOD1 mutation and prerandomization ALSFRS-R slope decline of at least 0.2/month.

Randomization will be stratified by 3 factors:

- whether a participant meets the prognostic enrichment criteria for rapid disease progression
- whether a participant uses edaravone at baseline
- whether a participant uses riluzole at baseline
  - Use of both edaravone and riluzole will not be a separate stratum but will be classified as only edaravone use.

Study Location:	Approximately 42 sites are planned in approximately 15 countries globally.
Number of Planned Participants:	Approximately 183 participants are planned to be dosed: 36 participants in Part A, 48 participants in Part B, and 99 participants in Part C.
Study Population:	This study will be conducted in participants who are at least 18 years of age with SOD1-ALS. Detailed criteria are described in Section 8.

CONFIDENTIAL

The information contained herein may not be used, disclosed, or published without the written consent of Biogen MA Inc.

Treatment Groups: Cohorts 1 through 4 (Part A) and Cohorts 5 through 8 (Part B) will be randomized to receive BIIB067 or placebo in a 3:1 (active:placebo) ratio. Cohort 9 (Part C) will be randomized to receive BIIB067 or placebo in a 2:1 (active:placebo) ratio.

Part A (SAD)

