#### **Part C: Full Participation Sites**

Randomization will occur only at full participation sites. It is planned to randomize approximately 99 participants total, of whom approximately 60 participants will meet the protocol-defined prognostic enrichment criteria for rapid disease progression (see Section 8.2.1).

CONFIDENTIAL

The information contained herein may not be used, disclosed, or published without the written consent of  
Biogen MA Inc.

Randomization will be stratified by the following 3 factors:

- whether a participant meets the prognostic enrichment criteria for rapid disease progression
- whether a participant uses edaravone at baseline
- whether a participant uses riluzole at baseline
  - Use of both edaravone and riluzole will not be a separate stratum but will be classified as edaravone use.

For participants in Part C (Pivotal), the study duration will be approximately 32-36 weeks including a 4-week screening period, a 24-week treatment period (3 loading doses 2 weeks apart followed by 5 maintenance doses 4 weeks apart), and a 4- to 8-week FU period as follows:

- Part C participants who enroll (uninterrupted) in the LTE study (233AS102): Week 28 Visit will serve as EOS Visit
- Part C participants with delays between their Week 28 Visit and enrollment in the LTE study: a Safety FU (Alternative EOS) Visit will be conducted (either in person or by telephone contact) to collect AEs, SAEs, and concomitant medications or procedures. This Safety FU (Alternative EOS) Visit can be performed at Week 32 or prior to (within 2 days) enrollment in the LTE, whichever comes first.
- Part C participants who do not enroll in the LTE study: Week 32 Visit will serve as EOS Visit (either in person or by telephone contact)

In the event of a decision by the Sponsor to terminate the study earlier on the grounds that conducting a placebo-controlled study is no longer deemed ethical based on the assessment of risk-benefit of Study 233AS101, all participants will be invited for an EOS Visit, during which all Week 28 assessments will be conducted. For participants not entering the LTE study or in the event the study is stopped early, there will be an additional safety FU visit 8 weeks after the last dose of study treatment.

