## 8.2. Part C (Pivotal)

### 8.2.1. Inclusion Criteria

To be eligible to participate in Part C (Pivotal) of this study, candidates must meet the following eligibility criteria at Screening, or at the timepoint specified in the individual eligibility criterion listed:

1. Ability to understand the purpose and risks of the study and provide signed and dated informed consent and authorization to use PHI in accordance with national and local participant privacy regulations. In the case that a participant is legally incapable of providing informed consent, the participant's legally authorized representative will be able to provide the informed consent.
2. Aged  $\geq 18$  years at the time of informed consent.
3. Weakness attributable to ALS and a confirmed SOD1 mutation.
  - a. SOD1 mutation must be confirmed by the central reader based on the sample obtained during the Screening Visit; participants with an SOD1 mutation interpreted by the central reader to be pathogenic or likely pathogenic will be eligible.
  - b. Additionally:
    - Prognostic enrichment criteria for rapid disease progression (participants may be eligible based on 1 of the following 2 criteria) [[Hamidou 2017](#); [Proudfoot 2016](#)]:

CONFIDENTIAL

The information contained herein may not be used, disclosed, or published without the written consent of Biogen MA Inc.

- a. One of the following SOD1 mutations and a prerandomization ALSFRS-R slope decline of  $\geq 0.2$  per month (calculated as [48-baseline score]/time since symptom onset):

p.Ala5Val, p.Ala5Thr, p.Leu39Val, p.Gly42Ser, p.His44Arg, p.Leu85Val, p.Gly94Ala, p.Leu107Val, and p.Val149Gly

**OR**

- b. SOD1 mutation other than those listed in item 'a.' with prerandomization ALSFRS-R slope decline of  $\geq 0.9$  per month (calculated as [48-baseline score]/time since symptom onset)
- Criteria for all other eligible participants: SOD1 mutation other than those listed in item 'a.' (no ALSFRS-R slope decline requirement).
4. For participants who meet prognostic enrichment criteria for rapid disease progression, SVC  $\geq 65\%$  of predicted value as adjusted for sex, age, and height (from the sitting position). For all other eligible participants, SVC  $\geq 50\%$  of predicted value as adjusted for sex, age, and height (from the sitting position).
- Note: For SVC testing, at least 3 acceptable tests with the 2 highest acceptable (largest and next largest) efforts within 150 mL of vital capacity should be achieved.

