#### Part C

For Part C, participants will be registered at Screening when a centralized IRT system will assign a participant identification number to each participant. Once a participant has been allocated an identification number, he or she is considered registered for the study. The participant's identification number will be used on all of that participant's CRFs and on all laboratory and other requisition forms. Any participant identification numbers that are assigned will not be reused even if the participant does not receive treatment.

If a participant is excluded from the study, the reasons for exclusion will be documented in the participant's source documents and on the screening log. Participants in Part C will be randomized on Day 1 after all predose assessments have been completed and after the Investigator has verified that the participants are eligible per criteria in Sections 8.2.1 and 8.2.2

CONFIDENTIAL

The information contained herein may not be used, disclosed, or published without the written consent of  
Biogen MA Inc.

and that all criteria to determine which stratum the participant should be randomized to have been correctly entered in the IRT system. These criteria include whether the participant meets the prognostic enrichment criteria for rapid disease progression, SVC, riluzole use, and edaravone use. No participant may begin treatment prior to randomization.

Eligible participants will be randomized in a 2:1 ratio to receive BIIB067 100 mg or placebo, respectively. Randomization will be stratified by 3 factors: 1) whether a participant meets the prognostic enrichment criteria for rapid disease progression; 2) whether a participant uses edaravone at baseline; and 3) whether a participant uses riluzole at baseline. Use of edaravone and riluzole will not be a separate stratum but will be classified as edaravone use.

Refer to the study reference guide for details on registration and randomization.

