- Summary statistics: difference between treatment groups in least square means of Day 197 change from baseline with corresponding standard errors and 95% confidence intervals taken from the ANCOVA for change from baseline to Day 197, based on the MI datasets. The ANCOVA model will include treatment group as a fixed effect and covariates for ALSFRS-R total score, baseline disease duration since symptom onset, and use of riluzole or edaravone.

For the JRT analysis, the ranked scores will be analyzed for each of the 100 MI-complete datasets using an ANCOVA model with treatment included as a fixed effect and adjusted for the following covariates: baseline disease duration since symptom onset, baseline ALSFRS-R total score, and use of riluzole or edaravone. The p-value will be based on combining the estimates for the treatment differences using PROC MIANALYZE. The difference between treatment groups in median changes from baseline to each visit will be presented with 95% confidence intervals based on the MI datasets, as well as the p-value from the JRT for Day 197. The joint rank analysis will only be performed for the mITT population.

The joint rank procedure allows for a statistical test of the treatment effect on the ALSFRS-R total score while accounting for truncation of data due to deaths. In this analysis, a participant's joint rank score will be calculated by comparing each participant to every other participant in the

CONFIDENTIAL

The information contained herein may not be used, disclosed, or published without the written consent of  
Biogen MA Inc.

study, resulting in a score of +1 if the outcome was better than the participant being compared, -1 if worse, and 0 if the same. The participant's score will then be calculated by summing their comparison to all the other participants in the study.

For the purpose of this calculation, participants will be grouped into the following 2 categories:

- Group 1: Participants who complete the study and have data available at the Day 197 assessment AND participants who withdraw from the study due to reasons other than death
- Group 2: Participants who die

MI will be used to impute all missing data before determining the rank score, including intermittent data and data after withdrawal from the study except after death.

In each of the 100 imputed datasets, participants will be ranked as follows:

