- Participants in Group 2 will be given lower ranks than participants in Group 1, with the lowest ranks being given to the participants who die in the shortest time after first dose. Progressively higher ranks will be given to participants who die at longer times after first dose.
- Participants in Group 1 will rank higher than participants in Group 2. Progressively higher ranks will be given to participants with a higher change from baseline at Day 197, i.e., a smaller decline at Day 197.

Further details will be described in the statistical analysis plan.

The primary inference will be based on the mITT population. The treatment comparison will be based on a 2-sided  $\alpha$  level of 0.05.

If the second scenario occurs, i.e., in both the active and placebo treatment groups combined the number of participants who died is  $< 3$  (e.g.,  $< 5\%$  deaths out of a total of 60 participants in the mITT population), the primary efficacy analysis will be the change from baseline in ALSFRS-R total score, analyzed using an ANCOVA based on data imputed using MI. The ANCOVA model will include treatment group as a fixed effect and covariates for each of the corresponding baseline value for ALSFRS-R total score, baseline disease duration since symptom onset and use of riluzole or edaravone. The primary inference will be based on the treatment comparison at Week 28. A 2-sided  $\alpha$  level of 0.05 will be used. Treatment differences at other visits will also be presented with nominal p-values.

Sensitivity, supplementary and subgroup analyses of the primary efficacy endpoint will be specified in the statistical analysis plan.

For the non-mITT population, the analysis will be the change from baseline in ALSFRS-R total score, analyzed using an ANCOVA based on data imputed using MI. The ANCOVA model will include treatment group as a fixed effect and covariates for each of the corresponding baseline value for ALSFRS-R total score, baseline disease duration since symptom onset, and use of riluzole or edaravone. Least square means with standard errors will be presented for each treatment group. The difference between treatment groups in least square means for change from baseline at each visit, with corresponding standard errors and 95% confidence intervals, will be presented with nominal p-values.

CONFIDENTIAL

The information contained herein may not be used, disclosed, or published without the written consent of  
Biogen MA Inc.

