The third secondary endpoint will be change from baseline to Day 197 in percent predicted SVC. If the number of deaths across both treatment arms is  $\geq 3$  (i.e.,  $\geq 5\%$  deaths out of a total of 60 patients in the mITT population), the primary inference will be based on the JRT methodology with MI to impute missing data; ANCOVA with MI for change from baseline will be used to obtain the estimates, and nominal p-values will be presented. If the number of deaths is  $< 3$  (i.e.,  $< 5\%$  deaths out of a total of 60 patients in the mITT population), ANCOVA with MI will be used as the primary analysis of this endpoint. The ANCOVA model will include treatment group as a fixed effect and covariates for baseline percent predicted SVC, baseline disease duration since symptom onset, and use of riluzole or edaravone. Treatment differences at other visits will also be derived from the model for exploratory purpose.

CONFIDENTIAL

The information contained herein may not be used, disclosed, or published without the written consent of Biogen MA Inc.

The secondary efficacy endpoints, time to death or permanent ventilation and time to death, will each be analyzed as time to event endpoints. Kaplan-Meier estimates of the cumulative probability of event occurrence over time will be determined. Treatment comparison will be based on a stratified log rank test. A Cox regression model will be used to obtain the hazard ratio and 95% confidence intervals for each of these endpoints. The analysis for each endpoint will also be repeated for the non-mITT population with nominal p-values presented.

[REDACTED]

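### Optional improvement, not an error: the primary mITT models for ALSFRS-R leave out listed-mutation status, which the entry rule treats as prognostic and which is not a stratification factor within the mITT

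*Protocol*

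**What the plan says.** Section 16.2.1.2.1 names the primary covariates itself and does not leave them to the SAP. The ANCOVA that supplies the estimate has "covariates for ALSFRS-R total score, baseline disease duration since symptom onset, and use of riluzole or edaravone". The rank ANCOVA of the joint rank test is "adjusted for the following covariates: baseline disease duration since symptom onset, baseline ALSFRS-R total score, and use of riluzole or edaravone". With fewer than 3 deaths the ANCOVA becomes the primary test, with "covariates for each of the corresponding baseline value for ALSFRS-R total score, baseline disease duration since symptom onset and use of riluzole or edaravone". The SVC model in Section 16.2.1.2.2 follows the same pattern: "covariates for baseline percent predicted SVC, baseline disease duration since symptom onset, and use of riluzole or edaravone".

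There are two routes into the mITT. The Synopsis gives a slope of at least 0.9/month "OR a protocol-defined SOD1 mutation and prerandomization ALSFRS-R slope decline of at least 0.2/month". Inclusion criterion 3b in Section 8.2.1 sets out the list ("One of the following SOD1 mutations and a prerandomization ALSFRS-R slope decline of" at least 0.2 per month) and asks carriers of any other mutation for at least 0.9 per month.

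Section 9.2 says "Randomization will be stratified by 3 factors: 1) whether a participant meets the prognostic enrichment criteria for rapid disease progression", and the other two factors are edaravone and riluzole use. Section 7.1.3 has the same first factor ("whether a participant meets the prognostic enrichment criteria for rapid disease progression"). That factor takes a single value inside the mITT.

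**The concern.** By its own entry rule the protocol treats a listed mutation as prognostic beyond the observed slope. Listed carriers qualify at 0.2/month, less than a quarter of the 0.9/month asked of others. Section 5.1 adds that progression differs between mutations, and Section 16.2.7 draws its survival assumptions partly on data for one mutation.

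Baseline score and disease duration together carry the prerandomisation slope, (48 - baseline)/duration, but not the flag. Someone with a slope between 0.2 and 0.9 looks slow on those covariates, yet was admitted because the mutation predicts fast decline. Nothing in the stratification or the model holds the listed share equal between arms of about 40 and 20.

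This single comparison gates every formal secondary test. If the shares happened to differ, a negative result could be blamed on an excess of listed carriers on active, and a positive one on an excess on placebo. An adjustment chosen after unblinding would settle little.

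**Working it through.** **Inputs from Section 16.2.7.** N = 60 in the mITT at 2:1, taken as 40 v 20; slopes -0.74 (active) and -3.83 (placebo), a difference of 3.09; SD 3.166; Week 28 survival 90% v 82%; two-sided 0.05; stated power 84%.

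**Assumptions, because the protocol gives no figure.** The share of the mITT with a listed mutation is 30-70%. The fraction R² of within-arm variance explained by the flag is varied from 0 to 0.10. No withdrawals are simulated.

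**1. The plan's own power.** The joint rank test was simulated with deaths ranked lowest by time. Without covariates power is 86.0%. With the three planned covariates and an uninformative flag it is 83-84%. The stated 84% is reproduced closely enough.

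**2. Chance imbalance (exact).** Let K of the 60 be listed and X of these fall on active, with X hypergeometric(60, K, 40). The difference in share is X/40 - (K - X)/20 = (3X - 2K)/40.

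| K (share) | 20+ points more on active | 20+ points more on placebo | Either |
|---|---|---|---|
| 18 (30%) | X ≥ 15: 6.5% | X ≤ 9: 6.9% | 13.4% (rounded once) |
| 30 (50%) | X ≥ 23: 8.5% | X ≤ 17: 8.5% | 17.0% |
| 42 (70%) | X ≥ 31: 6.9% | X ≤ 25: 6.5% | 13.4% (rounded once) |

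**3. Meaning of R².** With half the mITT listed, the gap between mutation groups is 3.166 × √(R²/0.25). R² = 0.05 gives 1.42 points/month, which is 1.42/3.09 = 46% of the assumed treatment difference.

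**4. Flag taken as independent of baseline score and duration (upper reference).** K = 30, power in % as planned v with the term:

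| Setting | All randomisations | Excess on active | Excess on placebo |
|---|---|---|---|
| R² 0 | 84.0 v 83.3 | 83.1 v 80.6 | 83.4 v 80.8 |
| R² 0.05, deaths unrelated to mutation | 83.0 v 83.1 | 75.1 v 81.5 | 89.3 v 81.5 |
| R² 0.05, deaths linked to mutation | 82.8 v 84.4 | 69.7 v 82.3 | 92.0 v 82.5 |

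Under the null, two-sided error over all randomisations is 4.8-5.2% with either model. In the randomisations with the excess on placebo, one-sided error favouring active (nominal 2.5%) is 4.3% as planned v 2.5% with the term. With deaths linked it is 5.9% v 2.5%.

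**5. Flag tied to prerandomisation slope, as the entry rule implies (the figures relied on).** The entry rule makes the flag correlate with slope, and the planned covariates already carry part of slope. With this link modelled under assumed slope distributions and a gap of 1.4 points/month, the effects shrink:
- Planned power is about 79% with the excess on active and 86-90% with the excess on placebo, against about 79-86% with the term.
- Planned one-sided error with the excess on placebo is about 4%.
- Adding the term changes average power by about -0.8 to +0.5 points if deaths are unrelated to mutation, and by about +1 if they are linked.

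**The case against.** The strongest reply is that nothing here is wrong. The covariate set is prespecified, keeps its level and roughly meets its stated power, and almost any omitted prognostic variable looks harmful once one selects the draws unbalanced on it. That stands, and it is why the point is optional. What sets this flag apart is that the protocol itself uses it to define the primary population.

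Second, the size rests on a listed share and a prognostic strength that the protocol never gives. A residual gap of 1.4 points/month is large beside 3.09. The flag pools nine mutations against all others, and the higher slope gate for unlisted carriers may bring the two routes closer in prognosis. This also stands, so the figures are shown for stated assumptions and the results of step 5 are preferred to those of step 4.

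Third, the primary analysis runs on 100 imputed datasets, so a flag added only to the analysis model would be an incomplete change. This is accepted, and the fix covers it.

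Fourth, the SAP may contain a mutation-adjusted sensitivity analysis. It may, but the primary covariates are fixed in the protocol.

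A reader might go further and infer that the arms will be unbalanced, that the primary test is biased, or that the term buys real average power. The documents support none of these. The flag is unstratified but randomised, the two-sided error stays at about 5%, and the average change is around zero. The wider swings in step 4 (70-92% power, 5.9% error) need both an assumed link between mutation and death and a flag unrelated to slope.

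**Conclusion.** The point holds as a cheap, prespecifiable safeguard and not as a defect. The primary mITT models omit a baseline flag that the entry rule treats as prognostic and that no stratum controls. Somewhere between one randomisation in eight and one in six (13-17%, for an assumed 30-70% listed share) would differ by 20 points or more between arms. If the flag carries a gap of about 1.4 points/month, the planned test then has about 79% power in one direction. In the other direction it has 86-90% power, with one-sided error of about 4% instead of 2.5%. If the residual gap is small, there is little to protect against and the term costs slightly. The protocol does not allow a choice between these cases, so confidence in the size is moderate and no average gain is claimed.

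**What to change.** Before unblinding, the sponsor could add listed-mutation status (yes/no, by the list in Section 8.2.1) as a covariate in:
- the mITT ANCOVA and rank ANCOVA for ALSFRS-R, in both death scenarios;
- the mITT SVC model in Section 16.2.1.2.2;
- the multiple-imputation models that feed these analyses.

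The flag should stay out of the non-mITT models, where it is constant because those participants all carry unlisted mutations. No change is proposed for the biomarker or other models, because no case was worked out for them.

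No new data are needed, since the mutation is centrally confirmed at screening. The change uses one of about 54 residual degrees of freedom (60 less intercept, treatment, two continuous covariates and two terms for three-level drug use). Because the covariates stand in the protocol, it needs an amendment with the submissions described in Section 19.4, as well as SAP wording. If the flag proves uninformative, average power falls by less than 1 point, and by about 1-3 points in the unbalanced randomisations.
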